## **Multiparameter Monitor Non-Invasive Blood Pressure Validation Study** **PR2019-329**

### **Synopsis**

#### **Purpose/ Objectives of the Clinical Investigation Plan**

The purpose of this study is to provide supporting documentation for accuracy claims for the Vital Detect blood pressure monitor on the intended adult population. A modified same arm sequential method with dual observer auscultation will be used to collect data.

The procedure, data collection methods and data analysis that are outlined in this protocol follow

- **International Standard ISO 81060-2:2018** Non-invasive sphygmomanometers — Part 2: Clinical investigation of automated measurement type

The end goal is to provide Non-invasive Blood Pressure (NIBP) accuracy data to support validation of the Vital Detect blood pressure monitor.

### **Background**

Automated blood pressure cuff measurement is the standard in numerous medical settings today. Oscillometric devices using deflation algorithms estimate the amplitude of pressure changes as the cuff deflates from above the systolic pressure. The amplitude suddenly increases as the pulse breaks through the occlusion of the artery. As the cuff pressure decreases further, the pulsations increase in amplitude, reaching a maximum level (which approximates the mean pressure), and then diminishes. Studies show that, especially in critical cases (arrhythmia, vasoconstriction, hypertension, shock), oscillometric devices are more accurate and consistent than devices using other non-invasive measuring techniques.

This study is designed to assess the accuracy of the Vital Detect blood pressure monitor with an adult population using a modified same arm sequential dual observer auscultation method and is considered investigational for this evaluation.

### **Summary Overview**

The Vital Detect blood pressure monitor will be evaluated in two phases, Phase 1 and Phase 2. Phase 1 will consist of 30 subjects that will approximate the distribution of blood pressures as outlined in **ISO 81060-2:2018**. Upon completion of Phase 1, an interim analysis will be performed to determine whether or not to proceed with Phase 2. Phase 2 will test a minimum of 55 additional subjects to achieve a minimum of 85 subjects. The maximum number of subjects enrolled will not exceed 150 subjects.

Two trained observers, typically a Registered Nurse (RN) or Licensed Practical Nurse (LPN), will observe (listen to) the Korotkoff sounds at the brachial artery of the arm. The reference blood pressure measurements by the nurses will be performed sequentially with the device under test. The nurses will complete 1 or 2 initial baseline auscultatory reference blood pressure measurements and device under test measurements. This is followed by 3 to 8 valid paired blood pressure readings of auscultatory reference blood pressure measurements alternated with device under test measurements. For accuracy claims, the test device measurements will be compared to those made by the reference device. The data for the final analysis will contain no fewer than 85 subjects with a minimum of 255 valid paired observations. At least 90% of the subjects will contribute 3 paired observations. In this case, additional subjects shall be used to complete the minimum number of paired observations.

#### **Subject Inclusion to the study:**

- Subjects must be able to provide an informed consent or have legally authorized representative consent to participate.

Clinimark [name], USA Site 001	TITLE: Multiparameter Monitor Non-Invasive Blood Pressure Validation Study Clinimark Study ID#: PR2019-329 Principal Investigator: [name]	DOCUMENT NUMBER PR# 2019-329 SHEET 3 of 22	REV 1
---	---	---	-----------------

- Subject must be willing and able to comply with the study procedures.
- Subject must be  $\geq 18$
- Subject or legally authorized representative must be able to read or write in English.
- Subjects with a finger circumference  $< 8.3$  cm.
- At least 30% of subjects shall be male and at least 30% of subjects shall be female

**Subject exclusion to the study:**

- Lack of Informed consent.
- Subjects with deformities or abnormalities that may prevent proper application of the device under test.
- Subject is evaluated by the investigator or clinician and found to be medically unsuitable for participation in this study.
- Subjects with known heart dysrhythmias
- Subjects with compromised circulation or peripheral vascular disease.
- Subjects with clotting disorders or taking prescribed blood thinners.
- Subjects that cannot tolerate sitting for up to 1 hour.
- Subject with a blood pressure demographic that has already been filled.

It is expected that the data collection will take up to 1 hour per subject and approximately 1-6 weeks to complete the evaluations. There is no additional follow-up required for the investigation.

**Purpose / Objectives of the Clinical Investigation Plan**

The primary purpose of this study is to provide supporting documentation for the Vital USA blood pressure monitor on an adult population using a modified same arm sequential, dual observer auscultation method. There are no risks or adverse device effects expected. There are no contraindications for use in the proposed study or study population.

**Identification and description of the investigational device**

The devices under test will be built according to the Vital USA design control processes.

The devices will include the Vital USA Vital Detect multiparameter platform with finger cuff.

**Vital Detect Multiparameter Platform Monitor**

Firmware	Version Number
NIBP (Non-Invasive Blood Pressure) Firmware	V10.0.15-48
Main	V5.0.3-1
Display	V1.0.11-20

Clinimark [name], USA Site 001	TITLE: Multiparameter Monitor Non-Invasive Blood Pressure Validation Study Clinimark Study ID#: PR2019-329 Principal Investigator: [name]	DOCUMENT NUMBER PR# 2019-329 SHEET 4 of 22	REV 1
---	---	---	-------

The Vital Detect blood pressure monitor is an investigational device. Device model numbers, serial numbers, date(s) of use, subject ID number(s) will be recorded on the Case Report Forms. A Device Accountability Log will be maintained for the sponsor's equipment documenting date of receipt, and date of return for used and unused product.

The intended purpose of the test is to evaluate the Vital Detect blood pressure monitor to **ISO 81060-2:2018**. The intended use for these products are manual and automatic Non-Invasive Blood Pressure monitoring on adults age 18 and older.

All appropriate testing has been performed and demonstrates safety and efficacy for use in human studies prior to Clinimark's receipt of the devices. Such documentation resides in the Design History Files at Vital USA. The device under test, the Vital Detect blood pressure monitor with finger cuff, is the only component expected to come in contact with the subjects.

The manufacturing of the device followed the good manufacturing practice regulation as identified in 21 CFR 820.

Instructions for installation, use, storage and handling can be found in the Vital Detect Manual.

Vital USA staff will train the Clinimark staff on the instructions for set up and use of the Vital Detect blood pressure monitor prior to start of the study.

### **Reference Study Equipment**

#### Reference Sphygmomanometer

The reference sphygmomanometer will be the Crystal Digital Sphygmomanometer. The device will be supplied by Clinimark to use for the duration of the study. The reference sphygmomanometer used in this study does comply with the requirements of ISO 81060-1, additionally the maximum error will be  $\pm 1$  mmHg per NIST traceable calibration verification.

#### Reference cuffs:

A released cuff (based on bladder size selection such as Baumanometer Calibrated V-Lok Cuff or Critikon Dura-Cuf or other).

The selection of the Reference cuff shall have a bladder length of 75% to 100% of the upper arm circumference and a bladder width of 37% to 50% of the upper arm circumference. If there is no reference cuff design that meets this requirement for an individual subject, a cuff that most closely meets these parameters will be selected.

#### Pulse Oximeter

GE 3900 TruTrak+ / OXYTip+ OXY-F-UN Sensor & Oxy-OL3 cable (cleared device K102426)

#### Stethoscope

3M Littman dual Auscultatory stethoscope or equivalent will be used in the study.

### **Preliminary Investigations and Justifications of the Study**

In review of the literature, **ISO 81060-2:2018** clearly defines the accepted guideline for conduct, documentation and evaluation of the accuracy of non-invasive automated measurement sphygmomanometer systems. This study is a full validation on the Vital Detect blood pressure monitor in an adult population following the guideline as appropriate for the **ISO 81060-2:2018**.

No Previous testing in the Clinimark laboratories were performed on the USA Vitals Multiparameter Monitor

Clinimark [name], USA Site 001	TITLE: Multiparameter Monitor Non-Invasive Blood Pressure Validation Study Clinimark Study ID#: PR2019-329 Principal Investigator: [name]	DOCUMENT NUMBER PR# 2019-329 SHEET 5 of 22	REV 1
---	---	---	-------

## **Risks and benefits of the Investigational device and clinical investigation**

Currently the FDA defines blood pressure devices as Class II devices CFR Section: 21 CFR §870.1130, Noninvasive Blood Pressure Measurement System. – Cardiovascular Diagnostic Devices. **The devices under test in this study are thereby considered non-significant risk devices.**

The device and use of the device under test does not meet the definition of significant risk device under 21 CFR 812.3(m)

For the purpose of this study:

It is not intended as an implant.

- The cuff is applied to the bicep and is removed following data collection, typically less than 1 hour

It is not purported or represented to be for use in supporting or sustaining human life

- These devices are not used to support or sustain human life.

It is not used for use of substantial importance in diagnosing, curing, mitigating, or treating disease, or otherwise preventing impairment of human health

- They are not used to diagnose, cure mitigate or treat disease.

The device as used in this investigation does not present a serious risk to the health, safety, or welfare of a subject.

- See below for discussion of risk associated with the device and use of the device.

There are no anticipated risks or adverse device effects to be assessed. There are no contraindications for use in the proposed study / study population (See description of Study Population below). There may be other risks to the subject associated with the device or procedure that are unforeseeable at this time.

### **Blood Pressure Cuff**

The reported risks associated with NIBP include: A) slight discomfort upon inflation of the cuff; B) possible bruising; C) petechial rash; and D) discoloration of the skin beneath the cuff. In rare instances the reported risks associated with NIBP include: A) peripheral nerve injuries; B) skin tear; and C) compartment syndrome (swelling of muscles in the limb causing the reduction of the blood supply to the muscle).

More than 3,946 adults, children, and newborn babies have had their blood pressures taken repeatedly in 104 studies using similar equipment. In these previous studies, the complications of taking repeated blood pressures were temporary and involved either bruising/rash; for example, petechiae rash (less than 2.2%), skin redness/lines (0.8%), or tingling/descoloration in the extremity wearing the cuff while the cuff is inflated (0.1%).

It is possible that the test subject may experience an allergic reaction to the material in the cuff. The Vital USA finger cuff in this trial utilize standard material that has undergone skin sensitivity testing.

### **ECG Electrodes**

Materials (such as the adhesives and/or gel contact) used in the electrodes may cause some skin irritation in some subjects. Typical skin irritations present with redness of skin and in some cases of sensitivity is an allergic reaction. Biocompatibility testing for surface contact electrodes is a requirement of the international Standards Organization (ISO) 10993- Biological Evaluation of Medical Devices. The risk in the use of ECG electrodes is believed to be minimal.

### **Pulse Oximetry Sensor**

Pulse Oximetry Sensor placement involves positioning pulse oximetry sensors on the volunteer subject in the same manner that is used on hospitalized patients. The sensors may be warm to the touch. Under normal operating conditions, (no fault conditions), the sensors are not expected to

Clinimark [name], USA Site 001	TITLE: Multiparameter Monitor Non-Invasive Blood Pressure Validation Study Clinimark Study ID#: PR2019-329 Principal Investigator: [name]	DOCUMENT NUMBER PR# 2019-329 SHEET 6 of 22	REV 1
---	---	---	-----------------

overheat. If the sensors are too warm, they will be removed immediately. Clip on sensors exert a minimal amount of pressure. They should not cause discomfort. If the sensors are too uncomfortable, they will be removed immediately. Adhesive sensors or tape may cause some irritations to the skin in some subjects. Every effort will be made to minimize products with natural rubber or latex. Products containing natural rubber or latex will be identified. The risk in the use of pulse oximetry sensors is believed to be minimal.

### **General Electrical Equipment**

Electrical hazards are a potential risk with all electrical equipment. The equipment used in this study has been designed to meet applicable safety standards. The equipment will be safety and functionally tested by the sponsor and institution (as indicated) prior to patient use. The possibility of any electrical hazard is extremely remote.

### **Benefits**

The benefits to the study are to the advancement of non-invasive medical monitoring of patients by improving Accuracy and performance of non-invasive blood pressure measurements. The only alternative to this study is to NOT participate.

## **Design of the Clinical Investigation**

### **Method**

The Vital Detect blood pressure monitor will be evaluated as a comparative, single center, non-randomized, study in a minimum of 30 subjects, conducted in 2 phases. The maximum number of subjects enrolled is 150 for both phases, to achieve 85 valid data sets. Each subject test is expected to take up to 1 hour. The overall data collection process is expected to be completed across 6 weeks.

The Auscultator will have a normal audiogram before the study begins. All experimenters will review the protocol prior to test.

Each subject or his/her legally authorized representative will be provided an IRB approved Informed Consent. As applicable, subjects will be told about any new information that might change their decision to participate. Subjects who have completed the informed consent and health questionnaire form and meet inclusion/exclusion criteria will be enrolled in the study if they meet desired blood pressure demographics. The study will be explained within his/her ability to understand.

Phase 1 will enroll a minimum of 30 qualified subjects into the study. Two trained observers will listen to the Korotkoff sounds at the brachial artery of the arm. The reference blood pressure measurements by the observers will be performed sequentially with the device under test. The device under test memory will be cleared prior to the next determination. In some cases, this may mean powering down the device to clear the previous readings. The observers will complete 1 or 2 initial baseline blood pressure measurements and then 3 to 8 paired NIBP measurements to be collected for the Accuracy evaluation will follow. Any pair of observers' determinations with a difference greater than 4 mmHg shall be excluded. If any determinations are excluded, additional pair(s) of determinations shall be taken to ensure that the needed number of valid test-reference pairs is collected (up to a maximum of 8 paired readings). In some cases, it may be that only 2 valid paired readings are achieved. This protocol allows for up to 10% of the subjects to have 2 valid paired observations (90% or more will contribute 3 paired observations). In this case, additional subjects shall be used to complete the minimum number of paired observations. A minimum of 85 valid paired NIBP measurements is needed for the final Accuracy analysis. The blood pressure measurements will be such that reference cuff measurements will be alternated with the device under test measurement. The auscultator will wait a minimum of 60 seconds between each blood pressure determination. Each observer's recording of observations of the reference sphygmomanometer shall not be visible to the other observer. The observers will record the exact measurement heard during auscultation and will not round the blood pressure readings. The readings of the sphygmomanometer-under-test shall not be visible to either of these observers. Each subject test is expected to take up to 60 minutes for the enrollment / data collection process.

Clinimark [name], USA Site 001	TITLE: Multiparameter Monitor Non-Invasive Blood Pressure Validation Study Clinimark Study ID#: PR2019-329 Principal Investigator: [name]	DOCUMENT NUMBER PR# 2019-329 SHEET 7 of 22	REV 1
---	--	--	-----------------

After data collection has taken place on a minimum of 30 subjects, an interim analysis will be performed. At this point Vital USA will have the option to continue with Phase 2 of the study, as long as no changes were made to the device. Phase 2 will be conducted in the same manner as Phase 1 (as outlined above), enrolling a minimum of 55 additional subjects for a total of at least 85 subjects.

There are no deviations expected from this investigation plan, should deviations be needed, discussions will be conducted with the sponsoring company, Principal investigator and the IRB will be notified per their requirements. Deviations from the study protocol will be disclosed in the final report.

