#### **Endpoint / Comparator**

The primary objective of this study is to provide a validation to **ISO 81060-2:2018** for non-invasive blood pressure measurement accuracy for the Vital Detect blood pressure monitor on the intended population. The Vital Detect blood pressure will be compared to the Reference Sphygmomanometer via a modified same arm sequential method with dual auscultators.

The final analysis will contain no fewer than 85 qualified subjects to achieve approximately 255 paired observations. The end goal is to pass the Criterion 1 and Criterion 2 of **ISO 81060-2:2018**.

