8. Record device information for tracking. (manufacturer, model #, serial or lot, hardware / software control info) on the Case Report Form (CRF).
9. Measure the circumference of the upper arm at the midpoint and place the appropriate sized reference blood pressure cuff on the bicep of the subject.
10. Attach the reference sphygmomanometer to the connector hose on the appropriate port on the reference blood pressure cuff.
11. Make sure the observers for the reference sphygmomanometer are positioned at a height level with the center of the manometer and within 15° from the centerline of the mercury tube (if used) so that parallax errors are avoided.
12. Both observers shall make an initial baseline reference blood pressure determination using a dual stethoscope. The last audible Korotkoff sound, fifth phase or K5, will be used for the diastolic blood pressure determination. Record which Korotkoff sound was used on the CRF. Record the baseline reference blood pressure reading on the CRF.
13. Apply the device under test on the subjects finger and follow the Instructions For Use (IFU).
14. Wait at least 60 seconds and then take the initial baseline device-under-test blood pressure determination. A third observer will record the data for the device-under-test and the reference values from the auscultators insuring that no pair differ more than 4 mmHg. These baseline data points shall not be used in the accuracy determination.
15. Make sure the previous reading of the device-under-test is cleared prior to the next reading.
16. For each subsequent blood pressure determination, wait at least 60 seconds between the readings.
17. The observers will start with the reference sphygmomanometer, then device-under-test, alternating until three valid paired blood pressure determinations are completed. The final reading should be on the reference sphygmomanometer. Make sure to wait at least 60 seconds between each of the readings.
18. The reference blood pressure determinations prior to the test device and post the test device will be averaged for the actual reference blood pressure determination of comparison.
19. Record each blood pressure determination and the pulse rate on the Case Report Form.
20. A maximum number of attempts for the subject is 8 paired determinations.
21. After three valid test-reference pairs are completed, the cuff will be removed.

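### The Method section sets the final-analysis minimum at 85 paired measurements, one third of the 255 pairs required elsewhere in the plan

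*Combined protocol and SAP*

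**What the plan says.** All references are to the combined protocol and SAP.

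- **Method, Phase 1 paragraph:** "A minimum of 85 valid paired NIBP measurements is needed for the final Accuracy analysis". Earlier in the same paragraph the same unit counts individual pairs within one subject: "then 3 to 8 paired NIBP measurements to be collected for the Accuracy evaluation will follow". The sentence just before the 85-pair figure is the top-up rule: "In this case, additional subjects shall be used to complete the minimum number of paired observations".
- **Method, opening paragraph:** the number 85 is attached to data sets: "The maximum number of subjects enrolled is 150 for both phases, to achieve 85 valid data sets".
- **Method, Phase 2 paragraph:** the number 85 is attached to subjects: "enrolling a minimum of 55 additional subjects for a total of at least 85 subjects".
- **Summary Overview:** "The data for the final analysis will contain no fewer than 85 subjects with a minimum of 255 valid paired observations". The top-up rule appears here too, shortly after the 255.
- **Endpoint / Comparator:** "no fewer than 85 qualified subjects to achieve approximately 255 paired observations".
- **Statistical Considerations:** the 85-subject and 255-pair minimums are both repeated. At most 10% of subjects may fall short of three valid determinations, with the balance made up from additional subjects. The example following Equation (3) gives n = 255 for an 85-subject study.

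**The concern.** The plan gives two different minimums for the number of pairs in the final analysis, 85 and 255. The lower one sits in the Method section, which staff follow when collecting data, and Phase 2 is to be run in the same manner.

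What is at stake is the top-up rule. When some subjects yield only two valid pairs, further subjects are to be added until the pair minimum is reached. Within the Phase 1 paragraph the only figure offered for that minimum is 85. Someone applying the rule from that paragraph to an 85-subject data set would conclude that no extra subject is needed, although the Summary Overview and Statistical Considerations would require one as soon as a single subject gives two pairs.

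**Working it through.** **Inputs**

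- Minimum subjects: 85 (Summary Overview; Method, Phase 2; Endpoint / Comparator; Statistical Considerations).
- Pairs per complete subject: 3. Up to 10% of subjects may give 2 (Method; Statistical Considerations).
- Minimum pairs: 255 (Summary Overview; Statistical Considerations), against 85 (Method, Phase 1).
- Enrolment cap: 150 (Summary Overview; Method).
- Collection ends at three valid pairs (Procedure, step 21): "After three valid test-reference pairs are completed, the cuff will be removed".

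**Step 1. Reproduce the plan's figure.** 85 subjects × 3 pairs = 255. This matches the Summary Overview, Statistical Considerations and the Criterion 1 example.

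**Step 2. Compare the Method figure.** 85 / 255 = 0.333, exactly one third. Reading the 85 as subjects or data sets restores 85 × 3 = 255, so a slip of unit is the likeliest cause. The document does not say so.

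**Step 3. Can 85 pairs describe the planned final analysis?** At three pairs each, 85 pairs need 85 / 3 = 28.3, so 29 subjects. The 30 Phase 1 subjects alone would give 30 × 3 = 90 pairs, or 27 × 3 + 3 × 2 = 87 with 10% at two pairs. The figure therefore does not fit an 85-subject final analysis.

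**Step 4. Would an 85-pair target ever trigger a top-up?** Suppose every one of 85 subjects gave only two pairs, far beyond the 10% allowance: 85 × 2 = 170, still twice the target. With 85 subjects in hand, it never would.

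**Step 5. When does the 255-pair target trigger one?** With N subjects, of whom k give two pairs and the rest three, pairs = 3N − k.

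- N = 85, k = 1: 255 − 1 = 254, short by 1.
- N = 85, k = 8 (10% of 85 is 8.5, so at most 8): 255 − 8 = 247, short by 8, and 8 / 255 = 3.1%.

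The smallest N with 3N − k ≥ 255 is 85 + k/3, with k/3 rounded up:

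| Two-pair subjects (k) | Subjects needed for 255 pairs |
|---|---|
| 0 | 85 |
| 1 to 3 | 86 |
| 4 to 6 | 87 |
| 7 to 8 | 88 |

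Check at k = 8: N = 86 gives 250, N = 87 gives 253, N = 88 gives 256. Ten percent of 86, 87 or 88 still allows at most 8 two-pair subjects. All these totals are within the cap of 150.

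**The case against.** The strongest reply is that the rest of the plan already settles the matter. The 85-subject minimum is restated in the very next paragraph of the Method section, and the statistical section gives both minimums. On that view this is one wrong noun, which the surrounding text corrects. That argument stands as far as consequence goes, and it is why the point is minor.

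Three further objections have some force:

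- **A per-subject reading.** Criterion 2 uses one averaged difference per subject, with m = 85 in its example, so 85 per-subject values do enter the final analysis. But the same paragraph uses the same unit for repeated pairs within one subject, which makes that reading a poor fit. If it was intended, the wording still needs changing.
- **The link to the top-up rule.** The rule also appears in the Summary Overview, where the nearby figure is 255, so a reader could trace its minimum there. The link to 85 comes from adjacency in the Method text. It is a risk of misreading, and the wrong figure does not formally control the rule.
- **The counts of 254, 247 and 86 to 88.** These show how the correct rule works and do not measure harm done. They also assume that complete subjects give exactly three pairs, whereas the Summary Overview speaks of three to eight valid readings.

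None of these makes 85 pairs agree with 255 pairs. The sentence names the final accuracy analysis, so it cannot be taken as an interim or Phase 1 minimum.

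**Conclusion.** The point holds and is minor. As written, the Method section understates the minimum number of pairs for the primary analysis by a factor of three. The probable cause is that 85 subjects or data sets became 85 paired measurements.

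Read as a whole, the plan does not permit a smaller final analysis, because the 85-subject and 255-pair minimums elsewhere still govern. The practical exposure is a missed top-up. At exactly 85 subjects the shortfall would be 1 to 8 pairs, at most 3.1% of 255, made good by one to three further subjects. These counts assume that collection stops at three valid pairs and that any subject below three contributes two. The contradiction between 85 and 255 depends on neither assumption. No effect on the chance of meeting Criterion 1 or Criterion 2 is claimed.

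**What to change.** In the Phase 1 paragraph of the Method section, restate the minimum as *at least 255 valid paired NIBP measurements from at least 85 subjects*. Both figures are already in the Summary Overview and Statistical Considerations.

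Optionally, and only for consistency, change the approximate 255 in Endpoint / Comparator to at least 255.

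The cost is the wording of one sentence, or two with the optional edit. Nothing changes in the design, the acceptance criteria, the planned sample size or the enrolment cap.
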